6.5.3 Vital Signs and Weight

The baseline value will be the last nonmissing value taken on or prior to first dose of study drug.

Vital signs (systolic blood pressure, diastolic blood pressure, pulse rate and body temperature) and weight will be summarized using mean, standard deviation, minimum, maximum and median by cohort (and overall) and visit. Additionally, a within-subject change will be calculated per visit as the postbaseline measurement minus the baseline measurement and summarized by cohort (and overall) and visit.

6.5.4 Electrocardiograms

ECG variables will be summarized using mean, standard deviation, minimum, maximum and median for each cohort and overall at each visit and time point, including changes from baseline. For subjects with replicate readings, mean value of replicate readings at each time point will be used in summaries.

Number and percent of subjects with normal, and abnormal results as assessed locally by investigator for overall interpretation will be tabulated by cohort and overall at each treatment visit and time point.

6.5.5 Pregnancies

A detailed listing of all pregnancies will be provided.

6.5.6 Eastern Cooperative Oncology Group Performance Status

Number of percentage of subjects for each category of the ECOG performance status at each assessment time will be provided by cohort and overall. ECOG performance status range from 0 (fully active) to 5 (dead). Negative change scores indicate an improvement and positive scores indicate a decline in performance. ECOG will also be summarized using shift table from baseline to maximum postbaseline score for each cohort and overall.

6.5.7 Ophthalmologic Assessment

The following ophthalmologic variables will be summarized by descriptive statistics and will be presented at each visit where ophthalmologic assessment is performed, by eye, cohort and overall:

- Visual acuity: method of assessment, visual acuity score (VAS)
- Slit lamp biomicroscopy: location of biomicroscopy, biomicroscopy interpretation (normal vs. abnormal)
- Tonometry: intraocular pressure result
- Dilated fundus examination: interpretation (normal vs. abnormal)

6.6 Analysis of Pharmacokinetics

Pharmacokinetic analysis will be conducted on the PKAS by cohort and overall.

Plasma concentrations of MMAE and serum concentrations of enfortumab vedotin will be summarized separately by scheduled time for each cohort and overall using descriptive statistics, including n, mean, standard deviation, coefficient of variation (CV), geometric mean, geometric CV, minimum, median and maximum. If appropriate, standard graphs of individual and mean trough concentration over time will be produced for each analyte by cohort and overall.

A separate population Pharmacokinetic Analysis Plan may be produced to describe potential model-based analyses. The results and the model development will be described in detail in a separate population pharmacokinetic report.

6.7 Interim Analysis (and Early Discontinuation of the Clinical Study)

For each cohort, one planned interim analysis will be performed to evaluate confirmed ORR at the time when 20 subjects had evaluable tumor response data per RECIST Version 1.1 by investigator assessment following study treatment. The interim analysis decision rule is based on Bayesian optimal phase 2 (BOP2) design [Zhou et al, 2017].

Specifically, let n denote the interim sample size and N denote the maximum sample size. For cohort i , let p_{0i} denote the reference ORR, p_{1i} denote the target ORR and $p_{eff,i}$ denote the treatment ORR of cohort i , and define the null hypothesis $H_{0i}: p_{eff,i} \leq p_{0i}$, representing that the treatment is inefficacious. At the time of the interim analysis for each cohort, the sponsor will stop enrolling subjects and claim that the treatment is not promising if

$$Prob(p_{eff,i} > p_{0i} | data) < \lambda \left(\frac{n}{N}\right)^\alpha,$$

where λ and α are design parameters optimized to minimize the chance of incorrectly claiming that an efficacious treatment is not promising (i.e., type II error) under the alternative hypothesis $H_{1i}: p_{eff,i} = p_{1i}$, while controlling the type I error rate at 0.1 (one-sided) (i.e., the chance of incorrectly claiming that an inefficacious treatment is promising is no more than 10%) for cohorts 1 to 8 and 0.025 (one-sided) for cohort 9. For this study, $\alpha = 1$ is selected for all 9 cohorts to have reasonable probability of early stopping, grid search was performed to identify an optimal λ for each cohort depending on their corresponding reference ORR (i.e., p_{0i}) and target ORR (i.e., p_{1i}). Optimal λ for each cohort is included in Table 3. Assuming a Beta(p_{0i} , $1 - p_{0i}$) prior distribution for $p_{eff,i}$, the above decision rules are corresponding to the following stopping boundaries:

Table 3 Optimal λ for Each Cohort

Cohort (Reference ORR vs. Target ORR) λ, α	Interim Analysis (Stage 1)		Final Analysis (Stage 2)	
	Number of Evaluable Subjects	Minimum number of Responders to Proceed to Stage 2	Number of Evaluable Subjects	Minimum number of Responders to Claim Promising Antitumor Activity
Cohort 1 ($p_{0i} = 0.2$ vs. $p_{1i} = 0.3$) $\lambda = 0.91, \alpha = 1$	20	4	40	12
Cohort 2/4 ($p_{0i} = 0.15$ vs. $p_{1i} = 0.25$) $\lambda = 0.885, \alpha = 1$	20	3	40	10
Cohort 3/5/6/7/8 ($p_{0i} = 0.1$ vs. $p_{1i} = 0.2$) $\lambda = 0.84, \alpha = 1$	20	2	40	7
Cohort 9 ($p_{0i} = 0.2$ vs. $p_{1i} = 0.45$) $\lambda = 0.98, \alpha = 1$	20	5	40	14

‡ Interim analysis for Cohort 6 will be conducted when applicable under protocol versions 1.0 and 2.0 based on enrollment status.

Based on the above table, using cohort 1 as an example, the sponsor will perform the interim analysis when the number of evaluable subjects with HR+/HER2- breast cancer reaches 20. If the total number of responders among the 20 evaluable subjects is less than 4, the enrollment of cohort 1 may stop; otherwise the enrollment will continue until the total number of evaluable subjects reaches the maximum sample size of 40. The sponsor will make the final decision on stopping cohort enrollment based on the overall evaluation of antitumor activity and safety data including subject's Nectin-4 expression data. At the final analysis, taking into account of overall antitumor activity (including central imaging data if available) and safety data, the sponsor will conclude that the treatment is promising if the number of minimum responders among 40 are met per Table 3; otherwise the sponsor will conclude that the treatment is not promising.

For each cohort, the interim analysis will be conducted when there are 20 subjects in RES per investigator assessment as defined in Section 4.2 are achieved. The interim analysis will include but is not limited to the following data:

- Demographics and baseline characteristics
- Disposition
- Medical and disease history
- Response related analysis including ORR, DCR, DOR, BOR and SOD per investigator assessment. Analysis based on BOR with confirmation and without confirmation will be provided.
- Available biomarker data
- Study drug exposure
- Adverse events, including SAE and AESI
- Laboratory data

The sponsor will review the interim data and make a decision on stopping/continuing the cohort enrollment. It is not the objective of the interim analyses to terminate the study early because of evidence of efficacy. Barring any unforeseen safety issues, the study is expected to continue until its scheduled completion. The details about sponsor review team membership, roles and responsibilities, data cleaning and data processing requirement will be described in a separate document.

6.8 Timing of Analyses

Interim analysis for each cohort will be conducted as specified in Section 6.7.

Primary analysis will be conducted for each cohort when all subjects in a cohort have had the opportunity to be followed for at least 6 months after the first dose of study drug. At the time of primary analysis for a cohort other than the last enrolling cohort, all data for that cohort up to data cutoff will be included. For the last enrolling cohort, the following data will be included:

- Efficacy data for the last enrolling cohort up to data cutoff date.
- Non-efficacy data for all subjects from all cohorts up to data cutoff date.

The final analysis of the study will be conducted when all subjects have discontinued from the study.

A Safety Monitoring Committee (SMC) will periodically monitor the study for safety and review study safety data for all cohorts. The details will be provided in the SMC charter.

6.9 Additional Conventions

6.9.1 Analysis Windows

CRF visits will be used for analysis. For safety analysis, in the case of multiple observations at a specific visit, the observation which is closest to the target date will be used. If the observations have the same distance to the target date, the latest one will be used. If more than one observation is made on the same day, an average value if continuous or the worst value if categorical will be included in the analysis.

6.9.2 Imputation Rules for Incomplete Dates

Every effort will be made to resolve incomplete death dates. If a partial date cannot be resolved, and subject's death status is Yes, the following imputation methods will be used to complete the missing information:

- If year and/or month is missing, death date will not be imputed. Subject will be censored at the last known alive date.
- If year and month are present but date is missing, death date will be imputed as the midpoint of the earliest and the latest feasible date when last known alive date and analysis cutoff date are taken into consideration, as the examples shown in the table below.

Incomplete Date of Death (YYYY MMM DD)	Last Known Alive Date (YYYY MMM DD)	Analysis Cutoff Date (YYYY MMM DD)	Imputed Date of Death (YYYY MMM DD)
2018 APR ??	2018 MAR 15	2018 MAY 01	2018 APR 15
2018 APR ??	2018 MAR 15	2018 APR 15	2018 APR 08
2018 APR ??	2018 APR 10	2018 MAY 01	2018 APR 20
2018 APR ??	2018 APR 10	2018 APR 20	2018 APR 15

In case of partial starting date of new anti-cancer therapy and new radiation therapy, the date will be imputed to the first day of the month but no earlier than the last dosing date of the study drug. A month and year must be present or the date will remain missing.

Partial or missing date of prior therapy: for start date, the date will be imputed to the first day of the month; for the end date, the date will be imputed to the last day of the month but no later than 14 days before the first dose of the study drug. A month and year must be present or the date will remain missing.

Missing or partial start and stop dates of AEs and concomitant medication will be imputed using the following algorithm:

- Imputation rules for partial or missing stop dates:

- If the month and year are present, then impute as the last day of that month.
- If only the year is present, impute as December 31 of that year.
- If the stop date is entirely missing, assume the event or medication is ongoing.
- Imputation rules for partial or missing start dates:

Start Date		Stop Date						missing
		Complete: yyyymmdd		Partial: yyyymm		Partial: yyyy		
		< 1 st dose	≥ 1 st dose	< 1 st dose yyyymm	≥ 1 st dose yyyymm	< 1 st dose yyyy	≥ 1 st dose yyyy	
Partial: yyyymm	= 1 st dose yyyymm	2	1	2	1	n/a	1	1
	≠ 1 st dose yyyymm		2		2	2	2	2
Partial: yyyy	= 1 st dose yyyy	3	1	3	1	n/a	1	1
	≠ 1 st dose yyyy		3		3	3	3	3
Missing		4	1	4	1	4	1	1

1 = Impute the date of the first dose; 2 = Impute the first of the month; 3 = Impute January 1 of the year; 4 = Impute January 1 of the stop year

The imputed dates will be used to determine whether an AE is/is not treatment emergent. Listings of AEs and concomitant medications will present the actual partial dates; imputed dates will not be shown.

Subjects who do not satisfy the criteria to be counted as responders or have insufficient data to determine or confirm a response per the RECIST guidelines (Version 1.1) will be considered as non-responders in the final analysis of response rates. No imputation of data will be done to determine individual subject response.

For continuous variables (e.g., clinical laboratory measurement, vital signs), subjects with missing baseline variable will be excluded from the analysis of change from baseline.

For all analyses other than pharmacokinetic analysis, all values will be included in the analyses. For analysis of pharmacokinetic data, only samples for which the time of sampling relative to the dose administration and the exact dose is known will be included.

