6.5 Previous and Concomitant Treatment (Medication and Nonmedication Therapy)

If the investigator determines that any of the following medications are necessary to provide adequate medical support to the subject, the subject must be withdrawn from further administration of the study treatment:

- Other investigational drugs
- Chemotherapy or other medications intended for antitumor activity. This does not apply to subjects on endocrine therapy, or to subjects on agents intended for the treatment of bone metastasis where subjects should be on a stable dose of bone targeting agents for at least 2 weeks prior to study entry (e.g., bisphosphonates, or receptor activator of nuclear factor kappa-B [RANK] ligand inhibitors).
- Radiation therapy except palliative radiation for nontarget lesions that is approved by the sponsor. Note: Radiation therapy to a preexisting symptomatic solitary lesion or to the bone may be considered on an exceptional case-by-case basis after consultation with the sponsor. The radiated lesion must be a nontarget lesion per RECIST Version 1.1 and the subject must have clear measurable disease outside the radiated field. Enfortumab vedotin may not be given concurrently with radiation therapy.
- Subjects who are receiving strong cytochrome P450 (CYP)3A4 inhibitors concomitantly with enfortumab vedotin should be closely monitored for adverse reactions.

- For cohort 9: Live or attenuated vaccines within 30 days prior to the first dose of study treatment and while participating in the study.
- For cohort 9: Systemic glucocorticoids except when used for the following purposes:
 - To modulate symptoms of an AE that is suspected to have an immunologic etiology
 - For the prevention of emesis
 - To premedicate for IV contrast allergies
 - To treat COPD exacerbations (only short-term oral or IV use in doses > 10 mg/day prednisone equivalent)
 - For chronic systemic replacement not to exceed 10 mg/day prednisone equivalent
 - For topical use or ocular use
 - Intraarticular joint use
 - For inhalation in the management of asthma or chronic obstructive pulmonary disease.

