confirmed disease progression per iRECIST as determined by the investigator, initiates a subsequent anticancer therapy, dies, withdraws consent, or the study closes. During study treatment, palliative radiotherapy on a nontarget lesion that is not progressing will not be considered a subsequent anticancer therapy; however, radiotherapy on any target lesion will be a subsequent anticancer therapy.

Copies of all imaging scans will be sent to the independent review facility in a timely manner. Central images may be read for a cohort after the minimum number of responders (confirmed ORR) at stage 1 based on the 2-stage BOP2 design are met per investigator assessment. Central images may also be read in certain circumstances as determined by the sponsor.

An end of treatment (EOT) visit will be performed within 7 days after the last dose of enfortumab vedotin or the decision to discontinue treatment, or prior to initiation of another anticancer therapy, whichever occurs earlier. This will be followed by a 30-day safety follow-up to be completed 30 days (+ 7-day window) from the last dose of enfortumab vedotin. The 30-day follow-up assessments should be completed prior to the initiation of another anticancer therapy.

Response (CR or PR) must be confirmed with a repeat imaging scan 4 weeks (28 days + 7-day window) after first response.

After radiologically-confirmed disease progression or initiation of subsequent anticancer therapy, whichever occurs first, subjects will be contacted every 12 weeks in the long-term follow-up period for survival status until death, withdrawal of consent, lost to follow-up or study closure, whichever occurs first.

Blood samples for pharmacokinetics and antitherapeutic antibodies (ATA) will be collected at protocol-specified time points. Validated assays will be used to measure the concentrations of enfortumab vedotin and MMAE in serum or plasma and to assess ATA. Samples for exploratory biomarkers will be collected at protocol-specified time points. Enfortumab vedotin biomarker assessments will not be used for subject selection.

Details of the schedule of clinical assessments are available in the protocol.

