5.2.3 Progression-free Survival per Investigator Assessment

PFS is defined as the time from the date of first dose of study drug to the date of first documented radiological disease progression (PD) per RECIST Version 1.1 by investigator assessment or death due to any cause, whichever comes first. PFS will be censored as the following:

- If a subject has neither PD nor death, PFS will be censored at the date of last evaluable radiological tumor assessment.
- If a subject starts a new anti-cancer treatment before any PD event or death, PFS will be censored at the date of last evaluable radiological tumor assessment prior to the date of new anti-cancer treatment.
- If a subject has PD or death immediately after two or more consecutive missed radiological tumor assessments, DOR will be censored at the last evaluable radiological tumor assessment prior to two or more missed radiological tumor assessments.
- If a subject does not have evaluable postbaseline radiological assessment, PFS will be censored at the first dose date of study drug.

For a subject who is censored, the last evaluable radiological tumor assessment refers to the subject's last radiological tumor assessment where the response is CR, PR or SD.

New anti-cancer treatment includes therapies captured on new anti-cancer therapy eCRF and new radiation/palliative radiation therapies captured on new radiation therapy eCRF that will impact target and/or non-target lesions.

PFS (in months) will be calculated as:

$$[(\text{Date of documented disease progression or death or censoring}) - (\text{Date of first dose of study drug}) + 1] / 30.4375$$

When a cutoff date is applied to PFS analysis, tumor assessment, death and new anti-cancer treatment occurring after the cutoff date will be excluded from the analysis.

The primary analysis population for PFS is FAS.

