5.2.5.1 Best Overall Response

BOR is determined based on all available timepoint tumor response data for a subject. Responses recorded after new anticancer therapy or PD will be excluded from BOR derivation.

BOR with Confirmation

Confirmation of CR or PR should occur at the subsequent assessment no less than 4 weeks following the initial assessment at which CR or PR is observed. BOR with confirmation will be derived according to below criteria per RECIST Version 1.1:

- If a subject has at least 2 CR and the first and the last CR dates are at least 28 days apart, then the BOR for this subject is confirmed CR.
- If a subject has PR and another CR/PR at least 28 days apart, then the BOR for this subject is confirmed PR.
- For those subjects who do not have confirmed CR or PR, if the subject has at least one tumor assessment record of CR/PR/SD which is at least 49 days after the first dose, then BOR is defined as SD.
- For subjects who do not have confirmed CR, confirmed PR, or SD, as defined above, but they have a tumor assessment of PD, their BOR is PD.
- Otherwise, BOR is defined as Not Evaluable (NE). For subjects without any postbaseline tumor assessment, BOR is defined as No Data (ND) which is a subcategory of NE.

BOR Regardless of Confirmation

The BOR regardless of confirmation for a subject is defined at the best timepoint tumor response in the order of CR, PR, SD, PD and NE. SD must be documented as present at least once at or after 49 days post first dose for BOR to be SD.

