Death or documented iUPD right after two or more consecutive missed disease assessments	Date of last disease assessment prior to the missed visits	Censor
None of the above	Date of last disease assessment on study	Censor

iPFS = Date of Event or Censor – Date of First Dose +1

New anti-cancer therapy includes therapies captured on new anti-cancer therapy eCRF and new radiation therapy eCRF.

For a participant who is censored, the last evaluable radiological tumor assessment refers to the participant's last radiological tumor assessment where the response is not NE.

When a cutoff date is applied to iPFS analysis, tumor assessment, death and new anti-cancer treatment occurring after the cutoff date will be excluded from the analysis.

5.3.3.5 iDOR

iDOR is defined as the time from the date of first documented response (iCR or iPR that is subsequently confirmed) as assessed by investigator to the date of first documented radiological disease progression per iRECIST or death due to any cause whichever occurs

first. iDOR will only be calculated for subjects achieving a confirmed iCR or iPR. The same censoring rules as described in Table 1 for iPFS will be applied for iDOR.

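### The last-dose floor in SAP 6.9.2 can date permitted on-treatment radiotherapy outside its recorded month, so DOR and PFS censoring is delayed or missed

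*SAP*

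**What the plan says.** SAP 6.9.2 has one rule for partial start dates, covering new radiation therapy and new anti-cancer therapy alike. It reads: "the date will be imputed to the first day of the month but no earlier than the last dosing date of the study drug". It applies only when the day alone is missing: "A month and year must be present or the date will remain missing".

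The date is used in three places.

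- **DOR and PFS (SAP 5.2.1, 5.2.3).** A subject who starts new anti-cancer treatment before progression or death is censored at the last evaluable scan before that start. The definition includes "new radiation/palliative radiation therapies captured on new radiation therapy eCRF that will impact target and/or non-target lesions".
- **iPFS, and iDOR by reference (SAP 5.3.3.4, 5.3.3.5).** "New anti-cancer therapy includes therapies captured on new anti-cancer therapy eCRF and new radiation therapy eCRF".
- **BOR, which defines confirmed ORR (SAP 5.2.5.1).** "Responses recorded after new anticancer therapy or PD will be excluded from BOR derivation". This section does not say whether radiotherapy is included.

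Protocol 6.5 lists treatments that require withdrawal from study treatment. Its radiotherapy entry carries an exception: "Radiation therapy except palliative radiation for nontarget lesions that is approved by the sponsor". For cohort 9, SAP 2.2 adds that during study treatment "palliative radiotherapy on a nontarget lesion that is not progressing will not be considered a subsequent anticancer therapy", whereas "radiotherapy on any target lesion will be a subsequent anticancer therapy".

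**The concern.** The floor assumes that the new therapy begins after study drug has ended. That need not be true of radiotherapy. A subject given approved palliative radiotherapy to a nontarget lesion is not withdrawn, so the last dose of study drug can come months later. If the site records only month and year, the rule overrides the month it does have and substitutes the last-dose date.

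Censoring for DOR and PFS is what is at stake. Scans after the radiotherapy are treated as if they came before it. A subject who should be censored at the last scan before radiotherapy stays at risk longer, or contributes a progression event that the plan's own definition would have censored. The other rules in 6.9.2 for a missing day do not do this: a partial death date is imputed within its month, and partial AE and medication start dates go to the first of the month or to the first dose.

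**Working it through.** The plan states no figure for this rule, so the check is date arithmetic under the rule as written.

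**Inputs.** Imputed start = max(first day of recorded month, last study-drug dose) (SAP 6.9.2). Scans every 56 days from first dose in cohorts 1 to 8 (SAP 2.2). PFS in months = (censoring or event date − first dose + 1)/30.4375 (SAP 5.2.3).

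**Step 1: size of the shift.** Assumed case: radiotherapy recorded as March 2024, last dose 15 September 2024. The rule gives 15 September. From 1 March that is 198 days; from 31 March it is 168. The start is therefore 168 to 198 days late, whatever the true day.

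**Step 2: effect on PFS censoring.** Assumed subject in cohorts 1 to 8: first dose 3 January 2022, last dose 12 September 2022, no progression. Scheduled scans fall on 28 February, 25 April, 20 June, 15 August and 10 October. Under the rule, a start in March, May or August is imputed to 12 September. The last earlier scan is then 15 August, and PFS is censored at 225/30.4375 = 7.39 months.

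| Recorded month | Start under SAP 6.9.2 | Days late | Scans after the recorded month but before the imputed start | PFS censored using first of recorded month |
|---|---|---|---|---|
| March 2022 | 12 Sep | 165–195 | 3 | 28 Feb: 57/30.4375 = 1.87 months |
| May 2022 | 12 Sep | 104–134 | 2 | 25 Apr: 113/30.4375 = 3.71 months |
| August 2022 | 12 Sep | 12–42 | 0 | 20 Jun: 169/30.4375 = 5.55 months |
| October 2022 | 1 Oct | none | 0 | 15 Aug: 7.39 months (unchanged) |

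For March the difference is 168 days, or 168/30.4375 = 5.52 months. For May it is 112 days, or 3.68 months. August shows the limit of a first-of-month convention: if radiotherapy really began after 15 August, that scan is legitimately pre-therapy, and the convention would censor one 56-day interval too early.

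**Step 3: when censoring is missed.** Take the March case with progression on the 15 August scan. Under the rule, progression precedes the imputed start and counts as an event at 7.39 months. With the start in its recorded month, the subject is censored at 1.87 months. The error therefore has no single direction for PFS or DOR: it can lengthen follow-up, or turn a censored time into an event.

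**Step 4: primary ORR, conditional only.** If one response were wrongly kept at n = 40, ORR would rise by 1/40 = 2.5 points. With interim minimum r1 and final minimum r (SAP Table 3), the two-stage type I error is Σ over x from r1 to 20 of P(X₁ = x)·P(X₂ ≥ r − x), where X₁ and X₂ are Binomial(20, p0). As planned this gives 8.5% (cohort 1), 6.6% (cohorts 2/4), 9.6% (cohorts 3/5/7/8) and 1.9% (cohort 9), all within the 10% and 2.5% limits in SAP 6.7. Replacing r by r − 1 gives 15.3%, 13.0%, 19.3% and 4.0%. These figures presuppose such a case. The documents do not establish that one would arise.

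**The case against.** The strongest reply is that the floor is sensible for most of what it covers. Starting a new anticancer therapy is a mandatory reason to stop study drug (Protocol 8.1), and radiotherapy outside the palliative nontarget exception also requires withdrawal (Protocol 6.5). For those therapies the true start should not precede the last dose, and the floor stops a first-of-month default from back-dating them into the treatment period. That stands; for them the rule fails only after a protocol deviation.

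A reader might go further and infer that the rule inflates the primary ORR, with shrinkage of irradiated lesions counted as response. The documents do not support that:

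- Permitted radiotherapy is to nontarget lesions, while PR is measured on the sum of target-lesion diameters. Irradiating a nontarget lesion does not itself reduce that sum. Clearing it could at most move a PR to a CR, and both already count.
- Target-lesion radiotherapy falls outside the exception and requires withdrawal, so dosing should not continue for months afterwards.
- SAP 5.2.5.1 does not say that radiotherapy is new anticancer therapy for BOR.
- SAP 6.9.2 itself says that data are not imputed to determine an individual subject's response, so the imputed date may not enter BOR at all.
- In cohort 9, SAP 2.2 exempts palliative radiotherapy to a non-progressing nontarget lesion.

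It can also be said that DOR and PFS are secondary and descriptive, and that few subjects will combine on-treatment radiotherapy with a missing day. Both are fair. They limit the importance of the point but do not remove it, because the rule still contradicts a month the site recorded and radiation is named explicitly in the DOR and PFS definitions.

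**Conclusion.** The point holds for DOR and PFS in a narrow form. A day-missing start of permitted nontarget radiotherapy, in a month before the month of the last dose, is dated outside that month. In the assumed examples the start is 12 to 198 days late, and PFS censoring moves by up to 5.52 months. It does not hold for dates in months after the last dose or, absent a deviation, for systemic therapy.

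In cohort 9 the position is unclear: the exemption in SAP 2.2 is not repeated in 5.2.1 or 5.2.3, and the iPFS definition counts everything on the radiation form. Any ORR effect would need both that radiotherapy counts for BOR and that imputed dates are used there, neither of which the SAP states.

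The conclusion assumes that on-treatment palliative radiotherapy is recorded on the new radiation therapy form. The wording of 5.2.1 and 5.2.3 suggests this, but the form is not in the documents. All example dates are assumptions. Frequency is not given and is probably low. The change is worth making because the fault lies in a stated rule and the correction is cheap.

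**What to change.** In SAP 6.9.2, separate the two therapies.

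- **New radiation therapy:** impute the first day of the recorded month, no earlier than the first dose of study drug and never outside the recorded month.
- **New systemic therapy:** keep the last-dose floor only when the last dose falls in that same recorded month.

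In SAP 5.2.5.1, state whether radiotherapy counts as new anticancer therapy for BOR. Reconcile that statement, and the definitions in 5.2.1 and 5.2.3, with the cohort 9 palliative-radiotherapy sentence in 2.2 and with the sentence in 6.9.2 against imputing for individual response.

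The cost is one derivation change and a few sentences, with no new data collection. The downside is that some DOR and PFS times will be censored slightly earlier than the true date would require: the imputed start can be up to 30 days early, which may drop a scan taken in the same month, as in the August example.
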